5.0 DETERMINATION OF SAMPLE SIZE

A total of 7500 subjects (3750 per treatment group) are planned to be enrolled in this study. The sample size will provide at least 90% power to meet a non-inferiority margin of 1.3 for the hazard ratio (febuxostat relative to allopurinol) of the primary endpoint. The sample size calculation assumed a true hazard ratio of 1.0 at a 1-sided 2.5% significance level with 3 interim analyses at approximately 25%, 50% and 75% of the events based on critical values obtained using the Lan-DeMets - O'Brien-Fleming alpha spending function.

For the determination of non-inferiority between the febuxostat treatment group and the allopurinol treatment group, the sample size calculation further assumed:

- Constant proportional hazards and exponential survival curves,
- Annual adjudicated MACE composite rate of 2.8%,
- Maximum length of participation of 5 years,
- Accrual time of 2.5 years, and
- Annual drop-out rate of 10%.

This study is designed to have a maximum of 624 MACE.

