An additional analysis on the primary safety endpoint will be performed using Cox-proportional hazards model controlling for the effect of NSAIDs use. The model will include treatment group, baseline renal function, and use of NSAIDs as explanatory variables. A similar analysis will control for the effect of low-dose aspirin use.

To identify risk factors an additional exploratory analysis on the primary safety endpoint will be performed using multivariate CPH modeling. The multivariate model will include treatment group and the following covariates jointly in the model with baseline renal function as the stratification factor: age, gender, BMI, NSAIDs use, low-dose aspirin use, smoking history,

baseline sUA, and history of diabetes, hypertension, non-fatal MI, or non-fatal stroke. No interaction terms will be introduced in the multivariate model. The backward elimination technique with a significance level to stay (SLS) in the model of SLS = 0.05 will be implemented for variable selection while always retaining treatment group and baseline renal function as stratification factor in the model.

In addition, the number and percentage of subjects with predefined MACE will be summarized within the levels of each subgroup variable. The relative risk (febuxostat versus allopurinol) and 95% CI based on the normal approximation will be calculated within the levels of each subgroup variable. Homogeneity among the levels of the subgroup variables will be assessed using the Cochran-Mantel-Haenszel test. A forest plot indicating the point and 95% CI estimates of the risk ratios within the levels of each subgroup variable will also be presented.

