6.12.2 Secondary Safety Endpoints

The following secondary safety endpoints will be assessed:

- The time from randomization to the first occurrence of any Antiplatelet Trialists' Collaborative (APTC) event (CV Death, Non-fatal MI, and Non-fatal Stroke).
- The time from randomization to the occurrence of each individual event in the pre-defined MACE composite.

Survival analysis using the CPH model will be performed on the time to the first occurrence of any APTC event and on the time to occurrence of each individual event in the pre-defined MACE composite. Parameter estimates and 2-sided 95% CIs for the hazard ratio will be computed. A graphical display indicating the point and 95% CI estimates of the hazard ratios for the primary MACE components will also be presented.

To identify risk factors for the time to first occurrence of APTC event, an exploratory analysis will also be performed using multivariate CPH modeling. The multivariate model will include treatment group and the following covariates jointly in the model with baseline renal function as the stratification factor: age, gender, BMI, NSAIDs use, low-dose aspirin use, smoking history, baseline sUA, and history of diabetes, hypertension, non-fatal MI, or non-fatal stroke. No interaction terms will be introduced in the multivariate model. The backward elimination technique with a significance level to stay (SLS) in the model of SLS = 0.05 will be implemented for variable selection while always retaining treatment group and baseline renal function as stratification factor in the model.

In addition, Kaplan-Meier plots for the time to first occurrence of APTC event and the time to first occurrence of each individual event in the pre-defined MACE will be presented by treatment group.

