At the DMC meeting on ^{PPD} [REDACTED], the 75% interim analysis results based on 468 adjudicated MACE for the primary MACE endpoint to assess cardiovascular safety was reviewed by the DMC. At the DMC meeting on ^{PPD} [REDACTED], the DMC informed Takeda that the non-inferiority criterion for the primary endpoint was met at the 75% interim analysis conducted in ^{PPD} [REDACTED]. According to the study design, the study should have been stopped and the non-inferiority of febuxostat relative to allopurinol with regard to cardiovascular risk should have been declared. However the DMC recommendation was to continue the trial without modification until the maximum 624 unique events were achieved to further assess all cause mortality (which was not a protocol specified endpoint) and CV mortality (which is specified only as a component of the MACE endpoint). Takeda agreed to follow the DMC recommendation and continue the study.

Based on the group sequential design, the 75% interim analysis will be the primary analysis for the primary MACE endpoint for the purpose of statistical inference. The continuation of the study to protocol-specified maximum events (624 unique MACE) is for the assessment of all cause mortality and CV mortality. The analyses of all cause mortality and CV mortality with and without death events after discontinuation of treatments will be added to the end of study analysis. An updated sensitivity analysis for the primary MACE endpoint based on 624 unique MACE will also be conducted to provide additional supportive evidence for the primary endpoint.

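### Minor: the exploratory MACE and APTC risk-factor models drop covariates that miss p<0.05 and plan no full-model display, so weak factors that survive would be overstated

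*SAP*

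**What the plan says.** Section 6.12.1 gives the MACE model's purpose and status: "To identify risk factors an additional exploratory analysis on the primary safety endpoint will be performed using multivariate CPH modeling". Section 6.12.2 does the same for APTC: "To identify risk factors for the time to first occurrence of APTC event, an exploratory analysis will also be performed using multivariate CPH modeling".

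Both sections enter treatment and the same covariates jointly, stratified by baseline renal function. The covariates are "age, gender, BMI, NSAIDs use, low-dose aspirin use, smoking history, baseline sUA, and history of diabetes, hypertension, non-fatal MI, or non-fatal stroke", which is 11 in all. The model is kept simple: "No interaction terms will be introduced in the multivariate model".

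Both sections then reduce it by the same rule: "The backward elimination technique with a significance level to stay (SLS) in the model of SLS = 0.05 will be implemented for variable selection". A covariate therefore stays only if it reaches p<0.05 and is otherwise removed. The only exemption is stated as "while always retaining treatment group and baseline renal function as stratification factor in the model".

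Neither section mentions shrinkage, resampling, selection-adjusted intervals or a display of the unreduced model. Neither says in words which covariate estimates will be tabulated. The general rule in section 6.1 makes tests and CIs two-sided at the 0.05 level unless something else is specified, and nothing else is specified here.

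**The concern.** The purpose of these two models is to estimate the covariates, and the covariates are what the selection rule distorts. A covariate stays only if its estimate lies at least about 1.96 standard errors from no effect. A weak factor can therefore appear only in exaggerated form. An ordinary 95% CI computed after that filter takes no account of it.

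Elimination is usually justified by too few events for the number of terms. Here the candidate list is short, fixed in advance and free of interactions, and the trial is event-driven with several hundred MACE. The rule therefore costs accuracy and appears to buy little. At stake is how the risk-factor tables are read: weak factors look stronger than they are, and moderate factors that narrowly miss 0.05 leave the final model. The treatment comparison is not at stake.

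**Working it through.** **Event counts.** Section 5.0 states: "This study is designed to have a maximum of 624 MACE". Section 6.13 refers to "the 75% interim analysis results based on 468 adjudicated MACE for the primary MACE endpoint" and makes that look the primary one for inference, so I use 468 and 624 as the range. The 624 reproduces. The Schoenfeld formula for a fixed design gives 4 × (1.960 + 1.282)² / (ln 1.3)² = 611 events. Simulating the four-look design with the Table 6.c boundaries gives power 0.901 at 624 events and overall one-sided alpha of about 0.025.

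**Events per parameter.** Treatment plus 11 covariates is 12 parameters. I assume up to 16 if some factors have more than two levels.
- MACE, 12 parameters: 468/12 = 39; 624/12 = 52.
- MACE, 16 parameters: 468/16 = 29; 624/16 = 39.
- APTC: the SAP gives no count. APTC is MACE without the urgent-revascularization component. If only half of 624 were APTC events (an assumption), 312/12 = 26 and 312/16 = 19.5.

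**Effect of the filter on one covariate.** Let Z ~ N(k, 1), where k is the true log HR in standard errors. The covariate is kept if |Z| > 1.96.
- Probability kept: P = Φ(k − 1.96) + Φ(−k − 1.96).
- Inflation of the log HR when kept: E(Z | kept)/k = [kP + φ(1.96 − k) − φ(1.96 + k)] / (kP).
- Coverage when kept, for 0 < k < 3.92: P(1.96 < Z < k + 1.96) / P.

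For k = 1: P = 0.1685 + 0.0015 = 0.170; inflation = (0.170 + 0.2516 − 0.0050)/0.170 = 2.45; coverage = 0.1435/0.170 = 0.84.

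For k = 2: P = 0.516; inflation = (1.032 + 0.3986 − 0.0002)/(2 × 0.516) = 1.39; coverage = 0.491/0.516 = 0.951.

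| k | Kept | Log HR inflated | Coverage when kept |
|---|---|---|---|
| 1 | 17% | 2.45-fold | 84% |
| 1.5 | 32% | 1.74-fold | 92% |
| 2 | 52% | 1.39-fold | 95% |

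**On the hazard-ratio scale.** Assume a binary factor with 30% prevalence. At 624 events SE = 1/√(624 × 0.3 × 0.7) = 0.087. Then k = 1 is HR exp(0.087) = 1.09, shown on average at exp(2.45 × 0.087) = 1.24 when kept; k = 2 is HR 1.19. At 468 events SE = 1/√(468 × 0.3 × 0.7) = 0.101, so k = 1 is HR 1.11, shown at about 1.28.

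**Check in full models.** Stratified Cox models were simulated with 7500 subjects, treatment and 11 independent covariates: 700 runs at about 621 events and 500 runs at 468. True HRs (1.0 to 1.5) and prevalences are assumptions, since the SAP gives none.
- Binary factors with HR 1.10, about 621 events: kept in about 17% of runs, mean HR 1.23 to 1.26 when kept, coverage 0.84 to 0.92. At 468 events the log HR was inflated 2.5 to 2.8 times, with coverage 0.74 to 0.85. These coverages rest on the minority of runs that kept the factor, so they are approximate.
- HR 1.15, about 621 events: kept in 27% to 41%, mean HR 1.24 to 1.31 when kept, coverage 0.94 to 0.96.
- HR 1.3 or more, both event counts: inflation 1.00 to 1.12, coverage 0.96 to 0.98.
- Treatment, forced in: unbiased, coverage 0.95 to 0.96.
- Full model without elimination: essentially unbiased, coverage 0.94 to 0.97 for every term.

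**The case against.** The strongest reply is that no decision rests on these models. Both are labelled exploratory. Non-inferiority is tested in a separate Cox model containing only treatment, stratified by renal function. Treatment can never be eliminated. The candidate list and threshold are fixed in advance, so the procedure is reproducible, and a full or reduced model for screening is partly a matter of preference. All of this stands, and it is why the point is minor. It does not make selection a good way to estimate risk factors when the full model is affordable.

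Second, the SAP never says that ordinary estimates will be reported for the survivors. That is correct. It is an inference from the section 6.1 default and from the absence of anything else. Elimination also starts from the full fit, and nothing forbids showing it. The point is that the plan does not commit to showing it.

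A reader might also infer three stronger claims that the documents do not support:
- That every interval in the reduced model is invalid. Undercoverage is marked only for weak effects and is gone by about k = 2.
- That elimination is what lets noise factors be called risk factors. The full model's 11 ordinary 95% CIs carry a comparable chance of a false exclusion of 1, so the fix would not cure that.
- That the event count is known to be ample for APTC. The SAP gives none; 312 is an assumption.

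**Conclusion.** The point holds as a minor one about an exploratory analysis. The plan removes any of 11 pre-specified covariates that miss p<0.05 and provides neither an adjustment nor a full-model display. If ordinary estimates are then shown, factors with true HRs around 1.1 are overstated roughly 2- to 3-fold on the log scale when kept, with coverage somewhere between about 74% and 92% depending on events and prevalence. Between there and about HR 1.2 the overstatement shrinks while coverage returns to nominal. At HR 1.3 or more the effect is negligible.

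The sizes rest on assumed prevalences and true HRs, on independent covariates, and on the inference that unadjusted estimates will be reported. The MACE event count supports the full model under either parameter count; for APTC that is likely but cannot be confirmed from the SAP.

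A reader might take this as a doubt about the cardiovascular safety conclusion. It is not: the primary analysis does not use this model, and the treatment term is always retained.

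**What to change.** In sections 6.12.1 and 6.12.2, make the full pre-specified model the main risk-factor result: treatment plus all listed covariates, stratified by baseline renal function, with hazard ratios and 95% CIs for every term. If the backward-eliminated model is still wanted, show it only as a supplement, labelled as the product of selection.

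The cost is a small wording change in each section and no new data; the full model is already the starting point of the elimination. The drawbacks are a longer table and slightly wider intervals where covariates are correlated. The primary analysis does not change.

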3.2 Study Design

This is a phase 3B multicenter, randomized, double-blind, active-controlled study designed to evaluate the CV safety of febuxostat compared with allopurinol in subjects with gout and significant CV comorbidities. Approximately 7500 subjects will be randomly assigned to study drug treatment.

The overall duration of the study is dependent on the number of predefined MACE. The length of the study is expected to be approximately 9 years. The length of study participation for each subject will vary due to the event driven study design. This study is designed to have a maximum of 624 MACE.

On Study Day 1, eligible subjects will be randomized in a 1:1 ratio to receive either febuxostat once daily (QD) or allopurinol QD. Randomization will be stratified based on baseline renal function (normal renal function or mild renal impairment versus moderate renal impairment). Baseline renal function will be defined using the following criteria based on estimated creatinine clearance (eCLcr):

- Normal renal function: defined as an eCLcr ≥ 90 mL/min.
- Mild renal impairment: defined as an eCLcr 60 to 89 mL/min, inclusive.
- Moderate renal impairment: defined as an eCLcr 30 to 59 mL/min, inclusive.

where estimated creatinine clearance (eCLcr) is calculated using the Cockcroft-Gault formula corrected for ideal body weight (IBW); IBW is 50 kg for males and 45.5 kg for women, plus 2.3 kg for each inch in height >5 feet (60 inches)]:

[figure not shown]
$$eCLcr = \frac{(140 - \text{Age}[\text{yr}]) \times (\text{IBW}[\text{kg}]) (\text{women multiply by } 0.85)}{72 \times (\text{serum creatinine} [\text{mg/dL}])}$$

Subjects randomized to febuxostat will initially receive the 40 mg dose QD. Subjects will remain on 40 mg for the remainder of the study if their serum uric acid (sUA) is <6.0 mg/dL at the Week 2 Visit. If their sUA is ≥ 6.0 mg/dL at the Week 2 Visit they will receive febuxostat 80 mg QD at the Week 4 visit, and will remain on this dose for the remainder of the study.

Subjects randomized to allopurinol who have normal renal function or mild renal impairment will initially receive allopurinol 300 mg QD with the dose increased in 100 mg increments monthly until either a sUA <6.0 mg/dL or an allopurinol dose of 600 mg QD is achieved. Subjects randomized to allopurinol who have moderate renal impairment will initially receive allopurinol 200 mg QD with the dose increased in 100 mg increments monthly until either a sUA

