6.12 Safety Analysis

Safety will be assessed by evaluating the incidence of adverse events including cardiovascular adverse events such as predefined MACE composite, and evaluating ECGs; laboratory tests and vital signs. A CV Endpoints Committee blinded to treatment assignment will adjudicate potential cardiovascular adverse events and each death to determine if it meets MACE criteria. The procedures and rules of adjudication of these events by the CV Endpoints Committee is described in a separate charter.

For the primary, secondary, and additional safety endpoints, time to event will be the time from the date of randomization or the date of last dose of study medication to the date of first occurrence of any event in the respective endpoint. If a subject reports an event for a given safety endpoint after treatment discontinuation, the reported event will be counted toward the treatment to which they were randomized. Subjects who are lost to follow-up during the study or who do not exhibit an episode of an event for the specific safety endpoint throughout the study will be censored at the day of last contact.

All safety endpoints will be analyzed using the Full Analysis Set (FAS). The FAS will consist of all subjects who were randomized and received at least one dose of double-blind study medication. Non-inferiority will be assessed only for the primary safety endpoint.

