6.12.1 Primary Safety Endpoint

The primary safety variable is the time from randomization to the first occurrence of any event in the predefined MACE composite. The goal of the primary safety analysis is to compare the risk of a predefined MACE during treatment with febuxostat to that of allopurinol.

Survival analysis using the Cox Proportional Hazards (CPH) model will be fitted on the time to the first occurrence of any event in the predefined MACE composite. The hazard ratio (febuxostat versus allopurinol) for the primary safety endpoint will be computed based on febuxostat and allopurinol estimated hazard rates. The febuxostat treatment group will be compared to the allopurinol treatment group to test for non-inferiority in the MACE composite rate using a CPH model with treatment as factor in the model and baseline renal function as a stratification factor. Non-inferiority of febuxostat to allopurinol will be declared (at an interim or at the final analysis) if the current upper 1-sided CI for the hazard ratio calculated with critical values obtained using the Lan-DeMets-O'Brien-Fleming alpha spending function, which preserves an overall 1-sided false-rejection rate of 2.5%, is less than 1.3.

Kaplan-Meier plot for the time to first occurrence of any event in the adjudicated MACE composite will be produced by treatment group (overall and within the levels of the stratification factor, baseline renal function).

A sensitivity analysis on the primary safety endpoint will also be performed by excluding MACE that occur more than 30 days after treatment discontinuation.

Assessment of the proportional hazards assumption will be made by inspection of the Kaplan-Meier curves and using plots of Schoenfeld residuals. In the Kaplan-Meier curves, if the proportional hazard assumption is satisfied then the graph of the survival function versus the survival time should result in a graph with parallel curves. In the plots of Schoenfeld residuals, if the proportional hazard assumption is satisfied then the graph of the Schoenfeld residuals obtained from the primary CPH model versus the ordered time of events along with smoothing spline should result in a horizontal line.

Alternative methods of analysis may be considered should some of the underlying model assumptions seem inappropriate (e.g., non-proportional hazards). The reasons for any changes to the planned approach and methods will be fully documented.

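### MACE effects in subgroups are planned as crude risk ratios that ignore follow-up time, although the treatment comparisons of time-to-event endpoints use Cox hazard ratios

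*SAP*

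**What the plan says.** SAP section 6.12.1 defines the endpoint as a time: "The primary safety variable is the time from randomization to the first occurrence of any event in the predefined MACE composite". Under section 6.12, subjects who are lost or have no event "throughout the study will be censored at the day of last contact". The treatment comparison is made "using a CPH model with treatment as factor in the model and baseline renal function as a stratification factor".

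For subgroups, the same section changes method: "the number and percentage of subjects with predefined MACE will be summarized within the levels of each subgroup variable". It continues: "The relative risk (febuxostat versus allopurinol) and 95% CI based on the normal approximation will be calculated within the levels of each subgroup variable". The display follows: "A forest plot indicating the point and 95% CI estimates of the risk ratios within the levels of each subgroup variable will also be presented".

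Elsewhere the SAP keeps to time-to-event methods. Sections 6.12.2 and 6.12.3 use Cox hazard ratios for APTC events, the MACE components and the additional time-to-event endpoints, and the component plot in 6.12.2 is on the hazard-ratio scale. The multivariate Cox model in 6.12.1 excludes interactions, so it yields no subgroup effects. The only other subgroup display of MACE is a set of Kaplan-Meier plots by level of baseline renal function.

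On follow-up, section 3.2 says: "The length of study participation for each subject will vary due to the event driven study design". Section 5.0 assumes "Annual drop-out rate of 10" percent.

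**The concern.** A crude proportion counts a subject lost after three months as event-free for the whole study. The ratio of two such proportions estimates the ratio of cumulative risks only if the arms are observed for similar lengths of time. If they are not, part of the ratio reflects observation time and not risk.

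This is a cardiovascular safety trial, and the forest plot is its only planned set of subgroup effect estimates. Readers will set those estimates beside the primary hazard ratio to judge whether it holds across subgroups. Unequal loss could make a subgroup look reassuring, or suggest harm, with no difference in the underlying hazard. The choice of homogeneity test is a separate matter; this point concerns the estimates and their intervals.

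**Working it through.** **Inputs.** From SAP section 5.0: MACE 2.8% a year, drop-out 10% a year, accrual 2.5 years, maximum participation 5 years, 7500 subjects, exponential survival. Read as annual probabilities, these give an event hazard λ = −ln(1 − 0.028) = 0.0284 and a loss hazard η = −ln(0.90) = 0.1054. With uniform accrual, potential follow-up T is uniform on 2.5 to 5 years.

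**Formula.** With s = λ + η, the expected proportion observed to have MACE is

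P = (λ/s) × (1 − m), where m is the mean of exp(−sT) = [exp(−2.5s) − exp(−5s)]/(2.5s).

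The crude risk ratio is P(febuxostat)/P(allopurinol).

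**The plan's own figure.** s = 0.1338 and m = 0.6084, so P = 0.2123 × 0.3916 = 0.08315. Then 7500 × 0.08315 = 623.6, which matches the planned 624. Setting η = 0 gives 756 events, so the planning model treats drop-out as lost MACE observation.

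**Results under the planning inputs** (allopurinol fixed at η = 0.1054, P = 8.315%):

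| True HR | Febuxostat η | Febuxostat P | Crude RR |
|---|---|---|---|
| 1.00 | 0.1054 | 8.315% | 1.00 |
| 1.00 | 0.13 | 7.965% | 0.96 |
| 1.00 | 0.15 | 7.697% | 0.93 |
| 1.30 | 0.1054 | 10.649% | 1.28 |
| 1.30 | 0.13 | 10.204% | 1.23 |
| 1.30 | 0.15 | 9.863% | 1.19 |

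Loss hazards of 0.13 and 0.15 are about 12% and 14% a year (1 − exp(−0.13) = 0.122; 1 − exp(−0.15) = 0.139). They are assumptions.

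**Where the shift comes from.** Expected observed time per subject is (1 − m)/s. At η = 0.13 it is 0.4443/0.1584 = 2.805 years, against 0.3916/0.1338 = 2.928 years on allopurinol. The ratio is 0.958, which is the whole of the distortion at a true hazard ratio of 1.0. Events divided by observed time give 0.0284 in both arms, so an analysis that uses time returns 1.00.

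**Longer study.** Section 3.2 expects about 9 years. Keeping 2.5 years of accrual (an assumption) puts T on 6.5 to 9 years. At 2.8% a year this would give about 1025 MACE, which conflicts with the maximum of 624. Lowering λ to 0.0166 (about 1.7% a year) gives 624. At a true hazard ratio of 1.0, febuxostat η of 0.13 or 0.15 then gives P of 7.685% or 7.221% against 8.320%, so crude RRs of 0.92 or 0.87.

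**Reverse direction.** With 8% annual loss on febuxostat and 12% on allopurinol, 2.8% MACE a year and T on 2.5 to 5 years, a true hazard ratio of 1.0 shows as 1.08.

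**The case against.** The strongest reply is that nothing in the SAP predicts unequal loss. It gives one drop-out rate for both arms. Section 3.2 has subjects who stop study drug but keep consent telephoned every 2 months until study end or MACE, so stopping treatment does not by itself end follow-up. This stands: only lost contact or withdrawn consent matters, and the size of the bias is conditional.

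A reader might infer four stronger points that the document does not support.

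- *That varying participation biases the ratios.* Administrative follow-up depends on entry date, which randomisation balances between arms.
- *That the plot misleads because it cannot be read against 1.3.* Section 6.12 limits non-inferiority to the primary endpoint, so no subgroup estimate is meant for that comparison. The scale difference alone is small (1.30 to 1.28).
- *That subgroups get no time-to-event display at all.* The Kaplan-Meier plots by renal function are one, though they give no effect estimate.
- *That unequal loss must create false heterogeneity.* A similar imbalance in every level shifts all the ratios by about the same factor. False heterogeneity needs loss that differs by arm and by subgroup level together, and nothing in the SAP indicates that.

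The shifts are also modest against subgroup precision. At 468 events, the basis of primary inference in section 6.13, half of the events give a 95% CI factor of exp(1.96 × 2/√234) = 1.29, and a quarter give exp(1.96 × 2/√117) = 1.44. That too stands, but wide intervals do not justify a method that adds avoidable bias when the better model is already specified.

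**Conclusion.** The point holds as an inconsistency of method with a conditional bias. The only planned subgroup effect estimates for a censored endpoint ignore censoring, while the SAP's treatment comparisons of time-to-event endpoints use Cox models.

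With equal loss the consequence is negligible. With febuxostat loss of about 12% or 14% a year against 10%, crude ratios fall by about 4% or 7% over the planned 5 years, and by about 8% or 13% over 9 years, in favour of the arm with more loss. These sizes rest on exponential times, non-informative loss, drop-out meaning lost MACE follow-up, and loss rates that the SAP does not state. They do not show that the trial's subgroup results are biased. The primary non-inferiority conclusion and its alpha are untouched.

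**What to change.** Replace the relative-risk sentence in section 6.12.1. Within each subgroup level, fit the primary Cox model (treatment as factor, stratified by baseline renal function; unstratified within the renal-function levels). Plot the hazard ratios with 95% CIs beside the overall primary hazard ratio. Keep the number and percentage with MACE as descriptive columns, and show counts only where a level is too sparse for a stable estimate.

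The cost is a sentence or two in the SAP and a by-subgroup run of a model already specified, with no new data and no alpha. The change removes bias from differential loss only where that loss is non-informative; loss related to MACE risk would still bias the Cox estimates.

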6.0 METHODS OF ANALYSIS AND PRESENTATION

6.1 General Considerations

The SAS System with the HP-Unix operating system, will be used to perform the statistical analyses. Unless otherwise specified, all statistical tests and confidence intervals (CIs) will be two-sided and conducted at the 0.05 significance level. All computations will be performed prior to rounding. Statistical significance will be determined using p-values which have been rounded to 3 decimal places. Unless otherwise specified, descriptive statistics on continuous variables will consist of the number of subjects (N), mean, standard deviation, minimum, 25th percentile, median, 75th percentile, and maximum.

For the purpose of this document study drug will refer exclusively to the double-blind treatment namely: febuxostat (40 mg QD or 80 mg QD) or allopurinol (200 mg to 600 mg QD in 100 mg increments). Unless specified otherwise all statistical tables will be presented by febuxostat and allopurinol treatment groups with no summaries by dose.

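### The Cochran-Mantel-Haenszel test named for subgroup homogeneity of MACE tests the average treatment effect, not whether the effect differs between levels

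*SAP*

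**What the plan says.** SAP Section 6.12.1 plans counts and percentages of subjects with MACE within the levels of each subgroup variable, and a forest plot. On the effect measure it says: "The relative risk (febuxostat versus allopurinol) and 95% CI based on the normal approximation will be calculated within the levels of each subgroup variable". The next sentence names the test: "Homogeneity among the levels of the subgroup variables will be assessed using the Cochran-Mantel-Haenszel test".

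Nothing else in the SAP tests whether the treatment effect varies. The only related statement concerns the exploratory Cox model in the same section: "No interaction terms will be introduced in the multivariate model". Section 6.1 sets the default that "all statistical tests and confidence intervals (CIs) will be two-sided and conducted at the 0.05 significance level", and this would apply to the subgroup test.

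**The concern.** The CMH null hypothesis is no association between treatment and outcome once the tables are stratified by subgroup level. The statistic adds the observed-minus-expected differences over levels, so opposite effects cancel and a common effect accumulates. A homogeneity test has to do the reverse.

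Two misreadings follow. Where subgroup effects truly differ but the average is near null, CMH is usually non-significant and would be reported as homogeneity. Where febuxostat is uniformly better, CMH can be significant and would be reported as heterogeneity. The first matters here because Section 6.13 records that "the non-inferiority criterion for the primary endpoint was met at the 75% interim analysis", which places the overall effect near null or in favour of febuxostat. In a cardiovascular safety trial, this would be the only formal statement on whether MACE risk differs between types of patient.

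**Working it through.** **Inputs.** Section 5.0: "A total of 7500 subjects (3750 per treatment group) are planned to be enrolled in this study". The design has "at least 90% power to meet a non-inferiority margin of 1.3 for the hazard ratio" and "assumed a true hazard ratio of 1.0 at a 1-sided 2.5% significance level with 3 interim analyses". Section 6.13 and Table 6.c give 468 events at the third look with critical value 2.359, and 624 events at the final look with 2.014. The SAP gives no subgroup sizes, so level sizes and true relative risks (RR) are assumptions.

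**The plan's own figure.** A fixed design needs 4(1.960 + 1.282)² / (ln 1.3)² = 611 events. Simulating the four looks with the Table 6.c boundaries, 624 events give 90.1% power and one-sided alpha 0.0252. The 624 reproduces, and the point below does not depend on it.

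**What meeting the margin implies.** With SE(log HR) ≈ 2/√468 = 0.0925:
- Largest observed HR that meets the margin: 1.3 × exp(−2.359 × 0.0925) = 1.045, z = ln(1.045)/0.0925 = 0.48. A significant CMH result toward harm is essentially excluded at that cut.
- A significant result toward benefit needs HR below exp(−1.96 × 0.0925) = 0.834.

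**Two examples with expected counts** (468 events, 1875 subjects per arm per level). CMH = [Σ(a − E)]² / ΣV, where a is febuxostat events and E half the level's events. For two levels, Q = (difference in log RR)² / (v₁ + v₂), with v = 1/a + 1/b − 2/1875 and b the allopurinol events.
- *Opposite effects, RR 0.7 and 1.3.* Allopurinol 117 and 117; febuxostat 81.9 and 152.1. Σ(a − E) = −17.55 + 17.55 = 0, so CMH = 0 and p = 1. Q = (0.262 + 0.357)² / (0.0197 + 0.0141) = 11.4, p = 0.0008.
- *Identical effects, RR 0.8 in both.* Allopurinol 130 and 130; febuxostat 104 and 104. Σ(a − E) = −26; V = 234 × 3516 / (4 × 3749) = 54.9 per level; CMH = 676/109.7 = 6.16, p = 0.013. Q = 0.

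**Rejection rates.** Binomial simulation, at least 40,000 trials per scenario, keeping only trials with log(A/C) + 2.359√(1/A + 1/C) < ln 1.3 at 468 events (A and C are total events per arm). Ranges cover two baseline assumptions: the same control risk in both levels, or the same pooled risk.

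| True RR by level | Split | CMH | Q test |
|---|---|---|---|
| 1.0 in both | 50/50 | 4% | 5% |
| 0.9 in both | 50/50 | 23% | 5% |
| 0.85 in both | 50/50 | 45% | 5% |
| 0.8 in both | 50/50 | 70% | 5% |
| 0.7 and 1.3 | 50/50 | 4-9% | 92-93% |
| 0.8 and 1.2 | 50/50 | 4-6% | 61-62% |
| 0.9 and 1.1 | 50/50 | 4% | 20% |
| 1.0 and 1.2 | 50/50 | under 1% | 17% |
| 0.7 (larger level) and 1.3 | 70/30 | 31-47% | 88-91% |
| 1.3 (larger level) and 0.7 | 70/30 | under 1% | 83-88% |

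Carried on to 624 events (75% of the risk accrued by the 468-event cut), RR 0.7 and 1.3 with equal levels give 4-10% for CMH against 98% for Q; RR 0.8 and 1.2 give 4-6% against 75%. In every row CMH follows the pooled effect and not the difference between levels.

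**The case against.** The best defence is that little hangs on this p-value. It enters no decision rule, and non-inferiority, alpha, the event count, the level-specific relative risks, their intervals and the forest plot are untouched. A reader could compute a Q test from the published intervals. All of that stands and limits the weight of the point. It does not make the named test the right one.

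A second defence is that a Breslow-Day test was meant, since software may print it beside CMH output. The text does not say so. That test compares odds ratios while the plan reports relative risks, but at overall risks of 468/7500 = 6.2% to 624/7500 = 8.3% the scale hardly matters: a Woolf test on odds ratios agrees with Q to about 0.1 to 0.2 percentage points. If Breslow-Day was intended, the sentence still needs correcting.

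Third, the large contrasts come from effects in opposite directions. For RR 0.9 and 1.1, or 1.0 and 1.2, the correct test is also usually non-significant (20% and 17% power). This is fair: the correct test gains most when the difference is large. Likewise, the false alarms need a true uniform benefit, which the SAP does not assume; at its planning value of 1.0, CMH rejects in about 4%.

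**Conclusion.** The concern holds. Followed literally, the sentence gives a p-value for average association under the label of homogeneity, and no other part of the SAP supplies the missing test. With equal levels and the margin met at 468 events, CMH detects RR 0.7 versus 1.3 in 4-9% of trials against 92-93% for a genuine test, and flags a uniform RR of 0.8 in 70% against 5%. These sizes rest on assumed level sizes and relative risks, on the planned critical value having been used, and on a two-sided 5% level; with unequal levels the CMH rate moves widely in either direction. The wrong hypothesis is a fact of the method and needs none of these assumptions. It should be corrected, but it has no bearing on the non-inferiority conclusion.

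**What to change.** In Section 6.12.1, replace the CMH test with the treatment-by-subgroup interaction test from the Cox model stratified by baseline renal function, including the subgroup main effect. That main effect is redundant only where the strata are the subgroup levels. Randomization uses two renal levels (Section 3.2) and the baseline summary three (Section 6.5), so the three-level version needs it. This test is on the hazard-ratio scale of the primary analysis, so the subgroup estimates and forest plot would best move to hazard ratios too. If relative risks stay the reported measure, use the Q test on log relative risks instead, which is the smaller edit. Either way, add that a non-significant result does not show homogeneity.

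The cost is one sentence and a little programming, somewhat more if the plot changes scale, and no new data. There are two drawbacks:
- **Timing.** The current SAP postdates the unblinded 75% interim, and Amendment 3 was written by the unblinded team (Sections 6.13 and 6.14.3). The change must be documented and made by authors still blinded to treatment, or labelled post hoc.
- **Power.** With SE = √(4/d₁ + 4/d₂), d₁ and d₂ being events per level, HR 1.0 versus 1.5 is detected with about 59% power at 468 events and 72% at 624 for a 50/50 split, and about 42% and 53% for 80/20.
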